1 PROTOCOL SUMMARY

1.1 SYNOPSIS

Title: Boost rTMS for AVH – Therapeutic Response and Neurobiological Prediction Markers in Auditory Verbal Hallucinations

Study Description: This is a randomized, placebo controlled, double-blind clinical trial. We aim to examine the efficacy of repeated transcranial magnetic stimulation (rTMS) for the treatment of auditory verbal hallucinations (AVH) in patients with schizophrenia who are not taking antipsychotic medication. We employ a novel, accelerated protocol with only 4 sessions of low-frequency rTMS in one day. The effects of this accelerated protocol will be compared to the sham stimulation. Additionally, we will examine the effects of rTMS on a neurophysiological level by evaluation mechanism of action in the temporo-parietal lobe.

Objectives: Primary Objective:
Examine the efficacy of low-frequency rTMS for AVH in patients with a schizophrenia spectrum disorder.

Secondary Objectives:
Examine the effects of rTMS on the quality of AVH, positive symptoms, general psychopathology, and the global level of functioning of these patients. Last, confirm that rTMS has no side effects on cognitive functioning.

Determine the neuroimaging-related biomarkers associated with response to rTMS using the baseline imaging parameters (rCBF, resting fMRI, T1, and DTI) to predict response to rTMS treatment. Further,

compare pre- and post-treatment imaging parameters (rCBF, resting fMRI, T1, and DTI) to characterize rTMS effects on AVH.

Endpoints:

Primary Endpoint:

- AVH assessed using the Hallucination Change Scale (HCS) at baseline (first visit), after the last TMS session, after the post-MRI.

Secondary Endpoints:

- a) Assessment of the qualitative content of hallucinations will be assessed using the revised Beliefs About Voices Questionnaire (BAVQ-R)
- b) Assessment of AVH as part of positive symptoms will be assessed with the Brief Psychiatric Rating Scale (BPRS)-subscale that includes "Hallucinatory Behavior", "Conceptual Disorganization", "Suspiciousness", and "Unusual Thought Content".
- c) Global functioning will be assessed using the Clinical Global Impression (CGI) and General Assessment of Functioning (GAF) questionnaires.
- d) Cognitive functioning will be assessed using the Repeatable Battery for the Assessment of Neuropsychological Status (rBANS).

Neurophysiological changes using magnetic resonance imaging (MRI) are investigated as predictors for rTMS treatment response.

Study Population:

N = 40

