1.2 SCHEMA

Prior to
Enrollment
Visit 1

Total N = 40; Obtain informed consent; Screen potential participants by inclusion and exclusion criteria; obtain history.

Visit 2
Time Point

Baseline assessments

- Clinical interview which includes as the Hallucination Change Scale, the Believes About Voices Questionnaire, the Brief Psychotic Rating Scale, the Clinical Global Impression, the Global Assessment of Functioning, and the Repeatable Battery for the Assessment of Neuropsychological Status.
 - Blood sample to determine antipsychotic concentration.
 - Baseline MRI measurement.

Visit 3
Time Point

Study intervention

4 sessions of rTMS within 1 day.

Visit 4
Time Point

Final Assessments

- Clinical interview including the same questionnaires as the baseline assessment.
- Post-treatment MRI measurement.

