If the total payment received from Northwell Health, during this year, is equal to \$600 or more, the payment is required to be reported to the IRS. Although this study does not pay \$600, if patients participate in other Northwell Health studies, it is possible their payment could end up totaling \$600. If this occurs, the payment received on this study will be reported to the IRS. In this case, patients will be issued a 1099 form and be required to provide their social security number at that time for reporting purposes. Patients will also be responsible for reporting this income while filing your tax return.

Compensation

	Screening Day	Baseline Assessment	Treatment Day	Follow-up Assessment
Visits	Visit 1	Visit 2	Visit 3	Visit 4
Procedures				
rTMS	None	None	Any weekday	None
MRI	None	1 st at baseline	None	2 nd after rTMS
Clinical Assessment & blood work	Yes	Yes	Yes	Yes
Compensation	\$20	\$50	\$0	\$50

Note that the Screening Day is not specifically set. This day can either be on the first day of the study such that patients who are willing to participate could start immediately with the baseline measurements. While patients who are for example recruited in the evening would have their first day of the study on the following day. In the special case of enrollment on a Friday, the start of the study would be the following Monday. Thus, patients would have to declare that they do not want to take antipsychotics during the weekend and the time of the study. See section 2.3.1 “Known Potential Risks” for information.

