8 STUDY ASSESSMENTS AND PROCEDURES

8.1 EFFICACY ASSESSMENTS

Rating

All assessments will be performed by trained raters.

Time frame

Screening procedures / evaluation must be done on the same day or the day before inclusion of the patient into the study. The reason for this is that we assess rTMS effect independently of potentially influencing antipsychotic medication effects. Therefore, patients cannot start with antipsychotic medication treatment parallel to the rTMS treatment. Clinical interviews will be conducted by trained staff.

Imaging

MRI acquisition will consist of the following: On the day of imaging, the patient will be transported to the North Shore University Hospital 3T Siemens Prisma MRI suite. The patient will undergo an approximately 55 minutes long acquisition session. All subjects will receive structural (e.g., T1) and functional (e.g. resting BOLD fMRI, DTI, and ASL) MRI exams. During the anatomical images, the participating subject will be asked not to move, during resting state fMRI, the subject will be asked to open their eyes and to think of nothing in particular, but to stay awake. The total scanning time will be approximately 55 minutes.

Assessment of instruments

The primary outcome measure is the improvement of AVH measured with the HCS.

The secondary outcome measures are:

- Qualitative outcome of the BAVQ-R
- AVH as part of positive symptoms measured with the respective BPRS-subscale
- Global functioning assessed using the CGI and GAF
- Cognitive functioning assessed using the rBANS

Structural and functional neurophysiological characteristics are investigated as predictors for rTMS treatment response.

Outcome criteria

Responder criteria:

- a. Clinically significant improvement is defined as a score of <8 on the HCS (Hoffman et al., 2013)
- b. Drop-outs: defined as patients who discontinue treatment before completing the 4 rTMS sessions.

Premature exits:

- a. Consent for study participation is withdrawn before 4 rTMS treatments have been administered, or
- b. rTMS is discontinued for clinical or other reasons before 4 rTMS have been administered, or
- c. Patient misses more than two treatments in total.

Both drop-outs and premature exits in this study will be analyzed as last observation carried forward.

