9.4.3 ANALYSIS OF THE SECONDARY ENDPOINT(S)

Our secondary goal is to test if rTMS improves also the quality of AVH (BAVQ-R), positive symptoms (BPRS-subscale), general psychopathology (CGI), and global functioning (GAF). Further, we want to confirm that rTMS has no impact on cognitive functions (rBANS).

Therefore, we will compute a number of repeated ANCOVAs with time of measurements as the within-subject factor, group (treatment vs. placebo) as between subject's factor, and baseline BAVQ-R scores, the positive symptom BPRS-scale, the CGI, and GAF scores as covariates, respectively. Patients who drop out of the study will not be included in the analyses. Further, we will compare the rBANS scores of baseline with the outcome scores within patients.

Additionally, we want to test if baseline neuroimaging biomarkers can predict response to rTMS. Therefore, voxel-wise multiple regression analyses in our neuroimaging measures will be performed to reveal areas and networks which correlate with the baseline scores of the HCS. We will calculate structural and functional connectivity analyses.

Preprocessing, and overview of the neuroimaging measures:

Baseline metabolic neuronal activity

The treatment effect will be monitored by assessing the baseline resting metabolic neuronal activity measured by ASL (Philipp Homan et al., 2011; Kindler et al., 2012; Orosz et al., 2012). Additionally, variations in resting CBF may be used as covariates of nuisance in all the analysis steps described so far.

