large-scale structure of the brain (Cabral, Hugues, Sporns, & Deco, 2011). Interestingly, RSN were found to be altered in disease population as compared to healthy controls (Bassett, Nelson, Mueller, Camchong, & Lim, 2012), indicating that the quantitative assessment of RSN may be a potential method for investigating psychiatric diseases (Meda et al., 2012) including schizophrenia (Ma, Calhoun, Eichele, Du, & Adali, 2012; Venkataraman, Whitford, Westin, Golland, & Kubicki, 2012). Of special interest for the current proposal will be the investigation of the language related functional network, also termed “working memory” or “language network” (Catani et al., 2011; Friederici, 2011; Friederici, Brauer, & Lohmann, 2011; K. Jann et al., 2012; Morgan, Mishra, Newton, Gore, & Ding, 2009).

Network connectivity is assessed through the measure of correlation coefficient (Zalesky, Fornito, & Bullmore, 2012). fMRI-BOLD image processing will be performed within SPM8 (<http://fil.ion.ucl.ac.uk>) and will include 3-D motion detection and correction using Levenberg-Marquarts’s least square fit for six spatial parameters, slice scan time correction through Sinc-interpolation. Co-registration of 2-D functional and 3-D structural measurements will be performed and normalization of data will lead to images in standard MNI space. All fMRI time-series will be further analyzed within the framework of Independent Component Analysis (ICA) using the Group ICA Toolbox (GIFT software) (Calhoun, Adali, Pearlson, & Pekar, 2001). We will compute subject maps (SMs) will be computed and identify temporally coherent networks (TCNs) by estimating maximally independent spatial sources. Finally, we will use a back-reconstruction method based on PCA compression and projection to estimate subject-specific SMs and TCNs for rest separately for all sessions (Erhardt et al., 2011). A subsequent t-test for the beta values corresponding to the rest and TMS condition will be computed (Arbabshirani, Havlicek, Kiehl, Pearlson, & Calhoun, 2013).

Structure of gray and white matter properties

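### Section 9.4.3 does not define the imaging treatment-effect analyses as a pre-to-post change compared between real and sham rTMS

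*Combined protocol and SAP*

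**What the plan says.** The Synopsis (1.1) gives as part of a secondary objective to "compare pre- and post-treatment imaging parameters (rCBF, resting fMRI, T1, and DTI) to characterize rTMS effects on AVH". Section 2.2.2 likewise presents MRI as an objective way to see what the treatment does to the brain.

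Section 9.4.3 then describes the measures one by one:

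- **ASL (cerebral blood flow):** "The treatment effect will be monitored by assessing the baseline resting metabolic neuronal activity measured by ASL".
- **Resting BOLD:** the back-reconstruction is used to "estimate subject-specific SMs and TCNs for rest separately for all sessions". The next sentence reads "A subsequent t-test for the beta values corresponding to the rest and TMS condition will be computed". Pairing, sessions and arms are not given.
- **FA (TBSS), VBM, cortical thickness, seed connectivity:** software and processing are named, but no contrast.

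On scheduling, the Schema (1.2) lists a "Post-treatment MRI measurement" at Visit 4. The visit table in 5.5 places the first MRI at baseline, none on the treatment day and the "2 nd after rTMS". In 8.1 the functional BOLD run is a resting one: "during resting state fMRI, the subject will be asked to open their eyes and to think of nothing in particular".

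The real-versus-sham factor is written out for the HCS (9.4.2) and for BAVQ-R, BPRS, CGI and GAF (9.4.3). It is written out for no imaging measure. The only imaging hypothesis in 9.1 (item 6) concerns prediction of response.

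**The concern.** The imaging objective is causal: it asks what rTMS does. Answering it takes a change over time and a comparison of that change with sham. Section 9.4.3 supplies neither clearly. A scan taken before treatment cannot carry a treatment effect, and a t-test against an undefined condition leaves the analyst to choose sessions, pairing and arm once the data are in hand.

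The most natural repair, a pre/post t-test, does not answer the question either. Participants are acutely ill inpatients scanned twice within a few days. Change from time, admission or repeat scanning would be credited to rTMS, and the sham arm is there to remove exactly that. Section 4.2 itself stresses the need for a sham group in TMS research.

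**Working it through.** **1. Which comparisons the scans allow.** Both 1.3 and 5.5 show no imaging on the treatment day, and 8.1 lists no run during stimulation. So the TMS condition cannot be a scan under TMS. The maps are for rest, one set per session. The reading that fits is rest after rTMS against rest before rTMS. (As it reads, the table in 1.3 also marks imaging at screening, where 5.5 shows none; this is one more reason to name the sessions.)

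**2. Where the sham arm enters.** Setting the analysis texts side by side:

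| Outcome | Sessions stated | Real versus sham stated |
|---|---|---|
| HCS (9.4.2) | time as within-subject factor | yes |
| BAVQ-R, BPRS, CGI, GAF (9.4.3) | time as within-subject factor | yes |
| ASL (9.4.3) | baseline only, read literally | no |
| BOLD networks (9.4.3) | rest and an undefined condition | no |
| FA, VBM, thickness, seed connectivity (9.4.3) | no | no |

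**3. What a missing sham contrast could cost (illustration).** The plan gives no figure for the imaging analyses. The only input taken from it is the 20 patients per arm in 9.2. That size reproduces: d = 0.9, two-sided 5% and 80% power give 20 per arm by the normal approximation. The exact noncentral t gives 20.39 per arm, with 79.2% power at 20.

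Assumption, not in the documents: rTMS has no effect on the measure, and both arms shift by the same amount δ, in SDs of the change score, for other reasons.

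- Pre/post t-test in the real arm: noncentrality = δ × √20 on 19 degrees of freedom. For δ = 0.5 this is 0.5 × 4.472 = 2.236.
- Between-arm test of change: the shift cancels (δ − δ = 0), so the noncentrality is 0 and the rejection rate equals the nominal 5%.

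| Assumed δ | δ × √20 | Pre/post test, real arm (n=20) | Between-arm test of change |
|---|---|---|---|
| 0.2 | 0.894 | 13.6% | 5% |
| 0.3 | 1.342 | 24.7% | 5% |
| 0.5 | 2.236 | 56.5% | 5% |
| 0.8 | 3.578 | 92.4% | 5% |

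These rates are for a single two-sided test of a single scalar measure.

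**4. The price of control.** In units of the SD of change, the standard error is 1/√20 = 0.224 for the one-arm test and √(2/20) = 0.316 for the between-arm difference. The ratio is √2, about 1.41.

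**The case against.** Several points on the other side are sound.

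- A reader might infer that no scan exists for the BOLD test. The documents do not support that: a resting scan after rTMS is scheduled in 1.2 and 5.5. It is the condition that is undefined; the data are not missing.
- A reader might infer that blood flow is measured only at baseline. The Synopsis lists rCBF among the pre/post parameters, 8.1 gives ASL to all subjects without restricting it to one scan, and the adjective may mean tonic resting perfusion. The fault lies in the analysis text, which literally conflicts with the objective.
- A reader might infer that the plan chose to leave out the control. It is silent on arm and pairing, and the permutation GLM for TBSS could hold a group contrast. The Synopsis and 4.1 say in general terms that effects are compared with sham.
- The drift values are assumed. Nothing in the documents shows drift of that size over three to four days. Pooling both arms would raise the rate (86.9% at 0.5 SD with n=40), but no section plans to pool.
- The trial calls itself an exploratory pilot, and imaging is mostly described as a predictor.

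These points limit the wording and the weight of the concern, but they do not supply the missing contrast. Nor can an uncontrolled reading be dismissed. Section 9.4.3 plans a within-patient comparison of rBANS, and section 2.1 still describes the rTMS as open-label.

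**Conclusion.** The point holds as a gap in specification. For no imaging measure does the plan define the treatment effect as a change compared between real and sham. Followed literally, the ASL sentence cannot show an effect. On its most natural reading, as a plain pre/post test, the BOLD test cannot separate rTMS from other causes of change.

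The size is conditional. Under an equal drift of 0.2 to 0.8 SD in both arms and no true effect, one uncontrolled test in the real arm errs in 14% to 92% of trials, against 5% for one between-arm test. The percentages show the direction and possible scale of the problem; they do not predict what this trial will find. Nor does the 5% extend to several measures or voxel-wise maps taken together.

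The change should be made, but it concerns a secondary, mechanistic objective. The primary HCS analysis, the group comparisons of BAVQ-R, BPRS, CGI and GAF, and the sample size are unaffected.

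**What to change.** In 9.4.3, replace the ASL sentence and the BOLD t-test sentence with one rule covering each imaging measure (CBF, connectivity, FA, grey matter): compare the post-treatment scan between real and sham, adjusted for the pre-treatment scan, or equivalently specify a group-by-time contrast. Name the two sessions compared. State separately that the prediction-of-response analysis uses the baseline scan as predictor; this does not stop the same scan serving as covariate in the treatment-effect analysis.

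The cost is SAP wording. Both scans are already planned in both arms, so no procedure or patient is added. The downside is lower power than an uncontrolled pre/post test: the standard error of a between-arm difference in change is about 1.41 times that of a one-arm change, though adjusting for the pre-treatment scan may recover part of this.

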
9.4.4 SAFETY ANALYSES

Safety endpoints will be analyzed as summary statistics during treatment.

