6.4 STUDY INTERVENTION COMPLIANCE

Compliance to study intervention is firstly confirmed by the patient signing the informed consent form. If patients do not want to continue treatment and finish all 4 rTMS sessions together with pre- and post-imaging and interviews, they will be excluded from the study which will be mentioned in the case report form. The data collected up to this point will not be included in the analysis because the primary outcome is the outcome measure of the HCS for which all three measures (baseline, after the last rTMS session, post-MRI) are necessary to reasonably estimate the symptom trajectory.

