7.2 PARTICIPANT DISCONTINUATION/WITHDRAWAL FROM THE STUDY

Participants are free to withdraw from participation in the study at any time upon request. Nevertheless, subjects may be prematurely terminated from the study if the investigators assess that the subject's clinical condition requires treatment(s) not available within the study context.

An investigator may discontinue or withdraw a participant from the study for the following reasons:

- Pregnancy as assessed with a pregnancy test before the two MRI measurements
- Significant study intervention non-compliance
- If any clinical adverse event (AE), laboratory abnormality, or other medical condition or situation occurs such that continued participation in the study would not be in the best interest of the participant
- Disease progression which requires discontinuation of the study intervention
- If the participant meets an exclusion criterion (either newly developed or not previously recognized) that precludes further study participation
- Participant unable to receive rTMS 4 times for one day
- If patients experience side effects that they are not willing to endure (such as headaches for example)
- Any medical condition which requires treatment with a medication with psychotropic effects
- Significant risk of suicidal or homicidal behavior (including aggressive behavior towards staff, others or themselves)
- MR Imaging contraindications
- Moving of patient or end of status as an in-patient at the Zucker Hillside Hospital

Duration of non-compliance will be determined by the trained study coordinator. Patients will be monitored closely by the study coordinator and all trained staff of the study. Changes i.e. in medication will be assessed before every visit/intervention.

If the patient had to have antipsychotics given because of an emergency or worsening of psychotic symptoms, then they are terminated from the study. However, we will also communicate on the ward that the patient's well-being is of main concern. Thus, should a patients' condition worsen and antipsychotics are thought to be the best help than medication should always be given regardless of the patient being enrolled in the study.

The reason for participant discontinuation or withdrawal from the study will be recorded on the Case Report Form (CRF). Subjects who sign the informed consent form and are randomized but do not

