8.3.4 TIME PERIOD AND FREQUENCY FOR EVENT ASSESSMENT AND FOLLOW-UP

The occurrence of an adverse event (AE) or serious adverse event (SAE) may come to the attention of study personnel during study visits and interviews of a study participant presenting for medical care, or upon review by a study monitor.

All AEs including local and systemic reactions not meeting the criteria for SAEs will be captured on the appropriate case report form (CRF). Information to be collected includes event description, time of onset, clinician's assessment of severity, relationship to study product (assessed only by those with the training and authority to make a diagnosis), and time of resolution/stabilization of the event. All AEs occurring while on study must be documented appropriately regardless of relationship. All AEs will be followed to adequate resolution.

Any medical condition that is present at the time that the participant is screened will be considered as baseline and not reported as an AE. However, if the study participant's condition deteriorates at any time during the study, it will be recorded as an AE. Thus, in the case of a worsening of symptoms leading to a worsening of the patient's condition, antipsychotic medication can be given on the ward if the responsible MD thinks that this is necessary for the patient's health. Patients' well-being is the main priority even if this means the termination from the study because of the antipsychotic.

Changes in the severity of an AE will be documented to allow an assessment of the duration of the event at each level of severity to be performed. AEs characterized as intermittent require documentation of onset and duration of each episode.

The PI as well as the research coordinator assisting the PI will record all reportable events with start dates occurring any time after informed consent is obtained until 7 (for non-serious AEs) or 30 days (for SAEs) after the last day of study participation. At each study visit, the investigator will inquire about the occurrence of AE/SAEs since the last visit. Events will be followed for outcome information until resolution or stabilization.

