8.3.5 ADVERSE EVENT REPORTING

Side-effects will be monitored by the study physician and self-reports. Treatment side effects will be measured using the Treatment Emergent Side Effects Scale (TESS). Reported adverse events will be evaluated and treated according to standard treatments procedures. In the case of a serious or intolerable adverse event subjects will be withdrawn from the study and he will be referred for treatment if necessary. Serious adverse events will be reported to IRB in no more than 24 hours after occurrence or after the psychiatrist is informed. In addition, this study will be fully compliant with the NIMH reportable events policy.

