9.3 POPULATIONS FOR ANALYSES

Data of all patients who attended pre-MRI and interview, 4 sessions of rTMS, and post-MRI and interview will be included in the analysis.

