9.4 STATISTICAL ANALYSES

9.4.1 GENERAL APPROACH

Descriptive statistics will include all patients who completed the study. Patient groups (stratified according to either their sham or real rTMS treatment) will be compared concerning age, sex, socio economic status, general psychopathology (CGI, GAF), severity of AVH (BPRS-subscale, BAVQ-R), and cognitive outcome (rBANS). In particular, mean (standard deviation) together with the range (min, max) will be assessed for the two groups.

Inferential statistics: the p-value will be set to 5% and therefore every value below this threshold is considered significant. Effect sizes will be calculated as well to evaluate if we are dealing with a clinically important effect. Covariates will be included in the analyses such as age and sex.

General assumptions of heterogeneity and normality will be assessed before any subsequent analysis. Based on this either parametric or non-parametric tests will be chosen.

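### The plan defines no safety population and plans no summary of events after participation ends, so patients withdrawn for side effects and late events have no stated place in the safety result

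*Combined protocol and SAP*

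**What the plan says.** Section 9.4.4 consists of one sentence: "Safety endpoints will be analyzed as summary statistics during treatment". It lists no safety endpoints, gives no denominator, does not ask for a comparison by arm, and does not say what period the last two words cover.

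Collection is much wider. Section 8.3.4 records events from consent "until 7 (for non-serious AEs) or 30 days (for SAEs) after the last day of study participation", and the schedule in Section 1.3 marks adverse event review at all four visits.

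On who is counted, Section 9.3 gives one population: "Data of all patients who attended pre-MRI and interview, 4 sessions of rTMS, and post-MRI and interview will be included in the analysis". Section 9.4.1 adds that "Descriptive statistics will include all patients who completed the study". For patients who do not finish all sessions, imaging and interviews, Section 6.4 says "The data collected up to this point will not be included in the analysis".

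On who leaves, Section 6.1.2 withdraws patients with limiting side effects. Section 8.3.5 says "In the case of a serious or intolerable adverse event subjects will be withdrawn from the study". Section 7.2 allows withdrawal for several reasons, among them "If patients experience side effects that they are not willing to endure" and suicidal or homicidal risk. It also says that patients who leave after receiving the intervention are replaced.

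Two passages point the other way. Section 7.1 says that stopping rTMS is not the same as leaving the study and lists data to collect at that point. Section 8.1 states: "Both drop-outs and premature exits in this study will be analyzed as last observation carried forward".

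**The concern.** The rule that fixes who is analysed is tied to harm. A patient who cannot tolerate the four sessions, or who has a serious event, leaves the study, falls outside the only population defined, and is replaced by someone else. The completer group can return to 20 per arm with nothing in the tables to show that anyone stopped. The time limit in Section 9.4.4 adds a second loss, because events in the 7-day and 30-day windows are recorded but no analysis is planned for them.

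This matters more here than in most pilots. Section 2.1 names safety as an aim and says that no study has examined the efficacy and safety of an accelerated low-frequency schedule, or rTMS for these hallucinations in unmedicated patients. A tolerability statement based on those who tolerated everything would be biased towards reassurance, and a larger follow-up trial might rely on it.

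**Working it through.** **Inputs.** 20 patients per arm (Section 9.2). Four sessions in one day (Section 1.2). Participation of 3 to 4 days (Section 1.1). Collection to 7 or 30 days after the last participation day (Section 8.3.4). Treated withdrawals are replaced (Section 7.2). The documents give no rate of stopping for side effects.

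**The plan's own figure.** The 20 per arm serves here only as a denominator. With effect size 0.9, two-sided 5% (sidedness is not stated, so this is assumed) and 80% power, the exact t calculation gives 20.39 per arm, and 20 per arm has 79.2% power. The normal approximation gives 20. The stated 40 in total is close enough and is not in dispute.

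**Time window.** Length of collection = participation days + follow-up days.
- Non-serious events: 3 + 7 = 10 to 4 + 7 = 11 days.
- Serious events: 3 + 30 = 33 to 4 + 30 = 34 days.
- If the summary covers the treatment day alone, it takes in 1 of 10 to 11 days and 1 of 33 to 34 days.
- If it covers all of participation, it takes in 3 to 4 days. The 7-day and 30-day periods still have no planned summary.

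**Denominator.** Assume that k active patients stop for side effects and each is replaced, so that 20 complete. Completers by definition include no one who stopped, so the completer rate is 0/20. The all-treated rate is k/(20 + k).

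| k (assumed) | Completers | All treated |
|---|---|---|
| 1 | 0/20 = 0% | 1/21 = 4.8% |
| 2 | 0/20 = 0% | 2/22 = 9.1% |
| 3 | 0/20 = 0% | 3/23 = 13.0% |
| 4 | 0/20 = 0% | 4/24 = 16.7% |

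**Does any other passage supply a safety denominator?**
- Section 8.1 carries forward the last observation for drop-outs. It sits under the efficacy outcome criteria, and it conflicts with Sections 6.4, 9.3 and 9.4.3, which leave those patients out.
- Section 7.1 keeps patients who stop rTMS in the study, whereas Section 6.4 excludes them. Neither says how their adverse events are counted.
- Section 6.4 justifies exclusion by the need for three HCS ratings. That is an efficacy reason and gives no ground for leaving out safety data.
- Section 10.1.6 has the principal investigator review all adverse events after each subject. This is oversight and produces no by-arm table.

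None of them does.

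**The case against.** The strongest reply is that the plan is silent on these points and excludes nothing. Section 9.4.4 does not contain the word only, and its time phrase could mean the whole 3 to 4 day participation. Sections 9.3 and 6.4 do not name safety, and Sections 7.1 and 8.1 contradict a blanket exclusion. Events are still recorded, reported and followed, withdrawal reasons go on the case report form, and the investigator weighs the frequency and severity of events. Worsening by the final visit in a completer would also show in the BPRS, BAVQ-R and CGI analyses.

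Much of this stands, and it rules out three stronger conclusions that a reader might draw.
- That next-day events are certainly dropped. This holds only if the phrase means the treatment day, which the text does not settle.
- That the tabulated count of serious events must be zero, because an early one leads to withdrawal and a late one falls outside the period. This needs the completer rule to govern safety, which the documents never say.
- That harm would go unseen. Collection and oversight continue; the loss is in the analysis.

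The reply does not supply what is missing. On either reading of the period, events after participation have no planned summary. On any reading of the populations, completers are the only group defined, and no passage puts withdrawn patients into a safety denominator.

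**Conclusion.** The point holds as a gap that leads to a biased safety summary if the stated rules are followed. The 7-day and 30-day events have no planned analysis, and patients withdrawn for side effects or serious events have no place in the only population defined. For 1 to 4 patients stopped and replaced in an arm, the reported stopping rate would be 0% where the rate among all treated is 4.8% to 16.7%. That range rests on assumed counts and on full replacement; the documents support no particular value. The ratio of 1 day to about 10 to 11 and 33 to 34 days rests on reading the period as the treatment day. The sponsor should correct this before analysis. It does not affect the sample size or the efficacy hypotheses.

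**What to change.** In Sections 9.3 and 9.4.4:
- Define a safety set of every patient who received any real or sham session, including those later withdrawn and replaced, and state that the completer restriction does not apply to safety.
- Summarise by arm the adverse events, serious adverse events, TESS results and withdrawals for adverse events, from the first session to the end of the windows in Section 8.3.4.
- Tabulate antipsychotic starts up to the final visit only. Section 5.5 expects antipsychotic treatment after the study, so later starts would mostly be ordinary care, and no collection of them is described.
- Reconcile Sections 6.4, 7.1, 8.1 and 9.3 on what happens to the data of patients who stop early.

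The cost is analysis-plan wording and an added table. There is one limit: Section 1.3 schedules no contact after Visit 4, so late events may be less completely ascertained than those at visits. The report should say so.
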